During extinction, participants will listen to audio recordings of the imagery scripts developed in Session 1. Participants receiving alcohol extinction will listen to their alcohol-related script; participants receiving soft-drink extinction will listen to their alcohol-unrelated script. Participants will also be given their preferred beverage along with empty commercial packaging; these will be the same during extinction as they were during retrieval, but during extinction, participants will not drink.

For all participants, cues will be presented in 5-min blocks: audio imagery scripts for 2 min, beverage exposure for 3 min. Once per min during the 3 min of beverage exposure, the participant will be instructed to take the glass in hand, raise it to his or her nose, and inhale its scent. Participants who drink any of the beverage during the extinction procedure will be discharged from the protocol.

There will be five blocks of cue presentation per session, with 5 min between blocks. In the time between blocks, the cues will be obscured from participants' view. Participants will fill out the one-item alcohol craving VAS if needed and will then be instructed to relax until the next block of cues. The alcohol craving VAS will be given three times during the extinction session: (1) immediately before the first block of cues, (2) immediately after the first block of cues, and (3) immediately after the fifth, final block of cues. The rating taken before the first block will be used to determine whether the beverage itself increased craving (Christiansen et al., 2013; Rose et al., 2014). To check that participants were successfully attending to the cues, following the last urge scale, participants may be asked brief open-

Abbreviated Title: Lab/GMA drinking

Version Date: 2/16/2022

ended questions about the session (e.g., “Tell me about what you did in today’s session...”). Participants will then be allowed to remain in the room and to relax for 20 min, at which point physiological monitoring will be ended, yielding a total extinction time of 65 min. During this period, participants will be given instructions to initiate progressive muscle relaxation and to focus on deep breathing, as after the script generation procedure. If participants are still feeling craving or otherwise “triggered” by the cues at the end of this period, they will receive counseling.

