Co-primary outcome 2: Reduction of craving and drinking in daily life. This will be analyzed in multilevel models, with the dependent variable operationalized in terms of participants' changes in alcohol craving and alcohol drinking in GMA reports after the four extinction-retrieval sessions, controlling for any preexisting differences. Because we cannot predict the time course of differential changes, our main analyses here will omit GMA data from the period when the four extinction-retrieval sessions are occurring. The dependent variable will be daily frequency of craving reports (or, in a separate analysis, daily number of drinks); the independent variables will be coded the same way as in the models for co-primary outcome 1, with experimental group (3 levels) dummy-coded so the experimental group is the reference level and a Wald test of joint significance can assess whether the experimental group differs simultaneously from both control groups. The continuous covariate will be each participant's overall frequency of craving or drinking during the baseline week of GMA.

Depending on the distribution of the dependent variable, we will use either general linear mixed models (e.g., SAS Proc Mixed) or generalized linear mixed models (e.g., SAS Proc Glimmix or SAS Proc NLMixed)—each of which provides a repeated-measures analysis that can handle missing days or early dropout and can accommodate person-level covariates, which will be included if they improve the fit of the model. These models use maximum-likelihood estimation and allow for specification of an

Abbreviated Title: Lab/GMA drinking

Version Date: 2/16/2022

autoregressive error structure (which can be tested against alternative error structures to provide the best-fitting model). In supplementary analyses, we will examine the time course of any differences that emerge during the period when the four extinction-retrieval sessions are occurring.

Secondary outcomes: Most of the other laboratory measures, such as self-reported craving and drinking at the 30-day follow-up visit, urine biomarkers for drinking, and heart-rate responses to cues, will be analyzed by an ANCOVA approach similar to the one used for the co-primary outcome measure 1. Analysis of the GPS component of the GMA data will be more exploratory, but will include testing for group differences in susceptibility to alcohol craving as a function of nearness to bars and liquor stores—a possible reflection of cue reactivity.

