3. Criteria for significance

Findings will be considered statistically significant at $p \leq .05$, two-tailed, with trends noted at $p \leq .10$.

J. Required Sample Size

We checked prior human studies to find likely effect sizes. For subjective drug craving, the difference between retrieval-extinction participants and control participants had a Cohen d of 1.12 (Xue et al., 2012, figure 3b, change scores for craving on day 4). In a prior human study on reinstatement of physiological reactivity to an extinguished (fear) cue, the difference between retrieval-extinction participants and control participants had a Cohen d of 1.11 (Liu et al., 2014, figure 1). These are large effects. We are powering our study for detection of effects that might be smaller. We used the module “Linear multiple regression: R-squared increase” in G*Power to determine what we could achieve with a realistic sample size. With evaluable data from 75 participants (25 in each of our 3 groups), we will have power of .80 to detect a Cohen f^2 as small as 0.13 on a test of the joint hypothesis that the intervention group differs simultaneously from both control groups in a linear regression model that also contains a covariate for baseline, at a two-tailed alpha of .05. An f^2 of .13 is approximately equivalent to a Cohen d of .61—conventionally considered a medium-sized effect. Despite the large effects seen in the prior studies, we think it is prudent to have power to detect a medium one.

Participants who drop out or are withdrawn from the study will be replaced. We anticipate that we will need to enroll 100 participants in order to have 75 complete the study.

K. Plans for Enrollment at Multiple Sites

Not applicable.

Abbreviated Title: Lab/GMA drinking

Version Date: 2/16/2022

L. Human Subjects Protection Plan

1. The responsibilities of investigators

Responsibilities and qualifications of investigators are given in the protocol appendix.

2. The names of investigators who will obtain informed consent

- [name].
- [name], MSc
- [name].
- [name].
- [name], MS
- [name]
- [name]

Non-FTE staff members will explain the consent form to participants under the direct supervision of a federal employee (FTE) who will sign the consent form.

3. Rationale for subject selection based on gender/ethnic/race categories at risk

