We will reduce the burden of carrying the portable electronic devices by providing participants carrying cases with belt clips. The risk of loss of confidentiality associated with carrying information on alcohol use on and location on smartphones will be minimized because the smartphones will have only coded identification numbers on them and will be password-protected. Many people now carry electronic devices, including smartphones, every day, and so it is not likely that the risk of robbery is substantially increased over the usual risks. We have issued smartphones or handheld computers to approximately 300 participants in prior studies without having encountered this problem. Similarly, all cell phones in the state of Maryland are now required to have position-tracking devices; therefore, risks from location tracking are similar to those of using a standard cell phone. All information we collect will be protected under an NIH-issued Certificate of Confidentiality.

Provisions for ensuring that necessary medical or professional intervention is available

Medical intervention will be provided by the Medical Advisory Investigator or nursing staff associated with the Treatment Section. Participants will also have access to trained psychological counselors. Participants will be able to contact medical staff and counselors during and between laboratory visits.

7. Subject monitoring

Parameters to be monitored

Abbreviated Title: Lab/GMA drinking

Version Date: 2/16/2022

BAC will be measured at the start of sessions 2-6 and then every 20 min after completion of study session tasks until BAC $\leq 0.01\%$ and participant may be discharged home by taxi or public transportation as described in “Study design” above.

Criteria for individual subject withdrawal

A participant will be withdrawn from the study if he or she:

- so requests, or withdraws consent.
- misses and does not reschedule any of the study visits.
- is unable or unwilling to complete study measures.
- does not complete at least 75% of GMA entries in two consecutive weeks.
- loses or damages two GMA smartphones.
- arrives at session with a BAL > 0 in more than two sessions
- develops any exclusionary condition or medical problem for which, in the MAI’s medical judgment, it is in the participant’s best interest to be withdrawn from the study.

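### The main daily-life analysis has no outcome data for anyone lost before the days after Session 5, so its claim to handle early dropout does not cover losses during treatment

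*Combined protocol and SAP*

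**What the plan says.** Section I.2, Co-primary outcome 2, takes its outcome (daily craving reports or daily drinks) from GMA after the four retrieval-extinction sessions. The baseline week enters as a covariate. On the treatment period it says "our main analyses here will omit GMA data from the period when the four extinction-retrieval sessions are occurring", because the time course cannot be predicted; those days go to supplementary analyses. It then says that each candidate mixed model "provides a repeated-measures analysis that can handle missing days or early dropout".

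Other sections decide who reaches that analysis:

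- **Section E.2, GMA data collection:** GMA ends at the start of Session 6.
- **Section A:** a participant is evaluable on completing GMA.
- **Section J:** "Participants who drop out or are withdrawn from the study will be replaced", with 100 enrolled to obtain 75 completers.
- **Section P:** the study stops at 75 completers.
- **Section E.2.b, Retrieval:** a second failure to complete the beverage leads to discharge.
- **Section E.2.b, Extinction:** "Participants who drink any of the beverage during the extinction procedure will be discharged from the protocol".
- **Section L.7:** a participant is withdrawn who "arrives at session with a BAL > 0 in more than two sessions".

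No all-randomised analysis set and no missing-data sensitivity analysis is described. The planned sensitivity analyses concern room ratings and participants who do not reach the expected BAC.

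**The concern.** A likelihood-based mixed model copes with dropout by using the outcomes a participant supplied before leaving. Here a participant who leaves during treatment has supplied no outcomes that the main model uses. Baseline days sit on the right-hand side of the equation and treatment-period days are excluded. The reassurance about early dropout thus fails for the whole span in which treatment is given.

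Replacement restores the number of participants but not the randomised comparison. If the reasons for leaving differ between arms and are related to drinking or craving, the groups compared after Session 5 can differ without any treatment effect. This matters because Section D would accept effects on the EMA measures alone as enough to establish efficacy.

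**Working it through.** **1. The plan's own figures.** Section J states that "we will have power of .80 to detect a Cohen f^2 as small as 0.13", "at a two-tailed alpha of .05", with 75 evaluable participants. For two tested group terms and one covariate, the numerator df is 2, the denominator df is 75 − 3 − 1 = 71, and λ = 0.13 × 75 = 9.75. Power from the noncentral F is .787, which agrees with .80 to within rounding. Enrolment also reproduces: 75 / (1 − .25) = 100. These figures are not in dispute; the point concerns who supplies data.

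**2. Who has an outcome row.**

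| GMA days | Role in main model | Lost before post-Session-5 days | Lost between Sessions 5 and 6 |
|---|---|---|---|
| Baseline week | covariate | available, but unused without an outcome | used |
| Sessions 2–5 period | omitted | collected, not used | not used |
| Session 5 to Session 6 | outcome | none | partial, used |

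A participant discharged at Session 5 also has no row. In a mock data set of 100 participants, 18 of them lost before Session 5, the post-period mixed model gave the same log-likelihood (−848.911) and identical coefficients with and without those 18.

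**3. How many.** The expected loss is 100 − 75 = 25. This is an upper limit for participants without rows. Section F counts completion of all six visits, so the 25 include losses after Session 5, and some may leave before randomisation.

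**4. Bias if loss is informative in one arm (assumptions).** There is no true effect and 34 are randomised per arm. Correlations are baseline–treatment .6, treatment–follow-up .7 and baseline–follow-up .6. Loss is random in the experimental arm. In the control arm, the heavier drinkers during treatment tend to leave, with correlation ρ between loss propensity and treatment-period level. For control loss p, with z the standard normal (1 − p) quantile, the control-minus-experimental bias is approximately

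−(.7 − .6 × .6) × ρ × φ(z)/(1 − p)

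- p = .25: φ(z)/(1 − p) = .318/.75 = .424. Bias is .34 × .424 × ρ = .043, .072, .115 for ρ = .3, .5, .8. Simulation with 25% loss in both arms gives .043, .076, .127.
- p = .30: .348/.70 = .497. Bias is .051, .084, .135. Simulation with 15% experimental and 30% control loss gives .051, .084, .148.

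All are negative: controls look better, which works against the intervention. Against the plan's stated d of .61, the range is .04/.61 = 7% to .15/.61 = 25%. Bias arises even at equal loss rates if the mechanism differs. With the same informative mechanism and 25% loss in both arms, bias is about zero and type I error .050 to .055.

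**5. Type I error of the joint 5% test, 75 completers (assumed losses).** The low end of each range is loss unrelated to outcome; the high end is a log-odds of loss of 1.5 per residual SD.

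| Loss: experimental / A / B | Type I error |
|---|---|
| 25 / 25 / 25% | .047–.055 |
| 30 / 15 / 30% | .048–.085 |
| 40 / 10 / 25% | .049–.152 |
| 35 / 5 / 35% | .048–.212 |

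The largest false contrast is .31 residual SD (.31 × .8 = .25 SD), experimental against A in the last row. It favours the intervention, so the direction depends on the assumption.

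**6. What joint modelling of all phases recovers.** In the cases of step 4, it leaves bias of .005 SD or less, but only because every dropout's treatment-period level was taken as fully observed. If half the dropouts lack it, about .01 to .06 remains. If loss depends on the follow-up level itself, the planned approach is biased by .08 to .25 and the joint model still leaves about .05 to .19.

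**The case against.** Much of the case for the plan stands.

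- **The sentence on dropout is not false.** It is correct for missed days and for dropout between Sessions 5 and 6, so it needs limiting, not deleting.
- **The plan does not declare a completers-only analysis.** Replacing participants is not the same as discarding their data, and someone with a few post-Session-5 days still contributes. Evaluable is a recruitment and sample-size term. The exclusion follows from the model's structure.
- **A reader might infer that exclusions are known to differ by arm. The documents do not show this.** The rules are worded alike for all arms and no loss rates by arm are given. The arrival-BAC rule is not arm-specific. The experimental group shares its retrieval drink with control B and its extinction condition with control A. Failing to finish a drink need not remove heavier drinkers.
- **The extinction beverage is itself unsettled.** Section E.2.b says it is the same as at retrieval, whereas the group definitions in Sections E.1 and E.2 cross the two for the control groups.
- **Omitting treatment days is a reasoned choice.** Dropouts supply mainly early treatment days, so treating those as a phase mean would assume a flat course.

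What remains is that losses during treatment have no outcome data in the main model, nothing else in the plan addresses them, and the rules give reasons why they might not be neutral.

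**Conclusion.** The point holds in limited form and should be fixed. The main co-primary 2 analysis handles missed days and dropout after Session 5, but not loss before then, which could involve up to a quarter of those enrolled. Bias of about .04 to .15 SD arises if loss follows treatment-period drinking in one arm only. It is near zero if loss is equal and works alike in all arms, or is unrelated to outcome. These sizes rest on assumed correlations and loss patterns.

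Two stronger readings are not supported. A reader might infer that the plan is biased towards the intervention, but without arm-specific losses the direction is unknown, and in the one-arm calculation it runs the other way. A reader might also infer that joint modelling would remove the problem. It reduces bias when dropouts have informative treatment days, and does less when they have few or when loss depends on unobserved follow-up drinking.

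**What to change.** 1. In Section I.2, limit the statement on dropout to missing days and dropout after Session 5.
2. Define an all-randomised analysis set that keeps replaced participants in their assigned groups. Report losses by arm and reason.
3. Fit one likelihood model to baseline, treatment-period and follow-up days as outcomes. Let group means be free in each phase, or in each inter-session interval because dropouts supply mainly early treatment days. Keep the follow-up-week group contrast as the estimate. Use this as the main analysis, or at least as a pre-specified sensitivity analysis beside the planned model.
4. Add a missing-not-at-random sensitivity analysis, for example by shifting the unobserved follow-up values by arm over a stated range.
5. Reconcile Sections E.1, E.2 (experimental groups) and E.2.b on the extinction beverage, so that it is clear what each arm's discharge rule acts on.

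The cost is SAP wording, slightly more modelling, and a missing-at-random assumption in the joint model that item 4 then tests. The treatment-period data are already collected and already used in supplementary analyses. No clinical rule needs to change for items 1 to 4.

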Stored biological specimens will be kept in a secure freezer in the Archway's NIDA freezer room until they are analyzed (BRC building; room 01B405). Specimens that are not used up in the analyses will be saved, but will not be used for any purpose not described in the protocol without prior IRB approval.

Urine samples will be kept in a secure freezer in the Archway's NIDA freezer room until they are analyzed (BRC building; room 01B405) and tracked by barcode. Those that are not used up in the analyses will be disposed of after the study. They will not be used for any purpose not described in the protocol without prior IRB approval. Any unplanned loss or destruction of the samples will be reported by the PI to the IRB.

I. Statistical Analysis

1. Outcome measures

Primary: (1) self-reported alcohol craving during the laboratory sessions, (2) GMA reports of alcohol craving and drinking.

Secondary: (1) self-reported alcohol craving and drinking at the 30-day follow-up, (2) heart rate during laboratory sessions and GMA collection periods, and (3) biomarkers for drinking, detected in urine samples collected during laboratory sessions.

2. Analysis of study outcomes

There are two ways in which we are performing multiple tests of statistical significance. First, we have two co-primary outcomes: a lab measure and an ambulatory measure. This design is actually conservative, because we will not consider US retrieval-extinction fully successful if it affects only the first outcome (protection from renewal/reinstatement in a lab setting) without affecting the second outcome (changes in daily-life behavior).

Second, we need to compare our experimental group to each of the two control groups—we expect the control groups to be similar to each other. If the experimental group differs from only one of the control groups, we will have to conclude that the effect of US retrieval-extinction did not actually require both retrieval and extinction, and thus worked via some unexpected mechanism. Although we might ultimately need to perform the two comparisons separately to explore unexpected findings, our main planned analysis is a single test of the joint hypothesis that the experimental group differs simultaneously from both control groups.

Our specific tests will be as follows.

Abbreviated Title: *Lab/GMA drinking*

Version Date: 2/16/2022

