Co-primary outcome 1: Protection from renewal/reinstatement of craving in session 6. We will analyze this in a linear regression model so we can control for a continuous covariate: each participant's mean level of craving in prior sessions (along with any person-level covariates that improve the fit of the model). To test the joint hypothesis that the extinction-retrieval group differs simultaneously from both control groups, we will dummy-code the 3-level predictor Group using two variables: Control Group A (0,1) and Control Group B (0,1), thereby making our intervention group the reference level. We will then perform a Wald test of the joint significance of the two Control Group predictors, maintaining an alpha of .05.

The dependent variable will be operationalized in terms of participants' ratings of alcohol craving in the renewal procedure and the reinstatement procedure from session 6. For each participant, we will generate a summary measure of renewal susceptibility (or, for separate analyses, reinstatement susceptibility) using within-session scores from session 6. For renewal, the score will be calculated as:

(pre-to-post-cue craving change in discordant room) *minus*
 (pre-to-post-cue craving change in concordant room)

For reinstatement, the score will be calculated as:

(pre-to-post-cue craving change after alcohol) *minus*
 (pre-to-post-cue craving change after soft drink)

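### Section J equates f² = .13 with d = .61, but with two like control groups it is about 0.76 residual SDs; .61 needs an unstated covariate correlation of about .60

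*Combined protocol and SAP*

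**What the plan says.** Section J of the combined protocol and SAP plans 75 evaluable participants, 25 in each of three groups, and uses the G*Power module for an R² increase in linear multiple regression. It says "we will have power of .80 to detect a Cohen f^2 as small as 0.13 on a test of the joint hypothesis", "in a linear regression model that also contains a covariate for baseline", "at a two-tailed alpha of .05". It then translates the effect: "An f^2 of .13 is approximately equivalent to a Cohen d of .61". It calls this medium-sized and sets it beside d values of 1.12 and 1.11 taken from two prior human studies.

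Section I.2 supplies the rest of the setting. The joint test is a Wald test of two control-group dummies, with the intervention group as reference. On the expected pattern of means it says "we expect the control groups to be similar to each other". For co-primary outcome 1 the covariate is each participant's "mean level of craving in prior sessions". The renewal outcome is a difference between two changes within session 6, of which the first is the "pre-to-post-cue craving change in discordant room".

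For the step from f² to d, section J gives no formula, pattern of means, SD basis or covariate–outcome correlation.

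**The concern.** In an R²-increase test, f² is the extra variance explained by the tested terms divided by the residual variance of the full model. Converting it to a difference between means requires a pattern of means and a choice of SD. Under the pattern the plan itself expects, the conversion gives a clearly larger d than .61, and no common shortcut gives .61 either.

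The figure matters because it is the only statement of the detectable effect on the same nominal scale as the cited 1.11 and 1.12. It also carries the claim that the study can detect a medium effect. A reader will take it that a true d of .61 has 80% power. If it does not, the margin built into N = 75 is overstated, and a null result could be read as stronger evidence against an effect of .61 than it is.

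**Working it through.** **Inputs.** From section J: N = 75, 25 per group, alpha .05, f² = .13, one covariate. From section I.2: two tested dummies and two controls expected to be alike. That makes three predictors, so the test has 2 and 75 − 3 − 1 = 71 degrees of freedom.

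**1. The plan's own power figure.** Noncentral F with λ = f² × N = .13 × 75 = 9.75 and df 2, 71 gives power **.787**. That agrees with .80 to within two points; exactly .80 needs f² = .134. The f² statement stands.

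**2. f² to d with two like controls.** Take means 0, d, d with equal n. The grand mean is 2d/3, so the between-group variance is (1/3)[(2d/3)² + (d/3)² + (d/3)²] = (2/9)d². In residual-SD units, with the covariate unrelated to group:

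- f² = (2/9)d², so d = √(.13 × 9/2) = √.585 = **.765**.

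**3. Other conversions of f² = .13 that might have been meant.**

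- Two equal groups, d = 2f: 2 × √.13 = .721.
- Extreme pair of three evenly spread means, f√6: .883.
- Eta used in place of f: .678 (two groups) or .720 (two like controls).

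None gives .61.

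**4. The unadjusted-SD reading.** If d is scaled on the within-group SD before covariate adjustment, and the covariate correlates r with the outcome, then d = .765 × √(1 − r²). The r that gives .61 follows from the f² of d = .61 at r = 0:

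- Like controls: (2/9)(.61²) = (2/9)(.3721) = .0827; r = √(1 − .0827/.13) = **.603**.
- d = 2f: (.61/2)² = .0930; r = √(1 − .0930/.13) = **.533**.

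**5. Power of the 2-df test at d = .61, N = 75.** The documents give no r, so r is an assumption shown over a range. The f² used is .0827/(1 − r²) for like controls.

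| r (assumed) | d matching f² = .13, unadjusted SD | f² at d = .61 | power, like controls | power, d = 2f |
|---|---|---|---|---|
| 0 | .765 | .0827 | .58 | .63 |
| .3 | .730 | .0909 | .62 | .68 |
| .5 | .662 | .1103 | .71 | .77 |
| .6 | .612 | .1292 | .78 | .83 |

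The r = 0 row also applies to a d of .61 expressed in residual SDs. A simulation of the ANCOVA with like controls (4,000 runs per setting) gave .56, .61 and .77 at r = 0, .3 and .6 for d = .61, and .79 for d = .765 at r = 0.

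**6. Scale.** .61/.765 = .80, an understatement of about 20%. Power of .80 at d = .61 residual SDs corresponds to N of about 120 (40 per group). At d = 1.11 and 1.12, taken as residual-SD values, power with N = 75 is .984 and .985.

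**The case against.** The strongest reply is that section J fixes neither the pattern of means nor the SD, so .61 is not impossible. The correlation it needs falls to about .55 if the SD includes between-group variance, and to about .53 under d = 2f. With no covariate correlation at all, .61 could be the smaller of two unequal differences if the other were about .86. Section J does not name the outcome either. For co-primary outcome 2 the covariate is the baseline-week frequency of the same behaviour, where a substantial correlation is more plausible, and further person-level covariates may be added. Finally, N was not derived from d: the operative claim is f² = .13, which reproduces, and the d is a gloss marked as approximate.

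Part of this stands. The required correlation is better described as roughly .53 to .60 depending on convention. The .58 is the end of a range that reaches .78. The SD basis of the cited 1.11 and 1.12 is also not given, so the power of about .98 at those values rests on an assumption.

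It does not rescue the sentence. Unequal controls contradict the expectation in section I.2. The linear regression described in section J matches co-primary outcome 1, where the covariate is a craving level and the outcome a difference of two changes; nothing in the documents supports a correlation near .60 between them. Every route to .61 depends on something the plan does not state.

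**Conclusion.** The concern holds: the f²-to-d conversion is wrong as written. With equal groups, like controls and a covariate unrelated to group, f² = .13 corresponds to about 0.76 residual SDs, not .61. The printed value can be defended only in unadjusted-SD units with a covariate–outcome correlation of about .60 (about .53 under d = 2f), which is neither stated nor supported. Power at d = .61 with 75 participants is between .58 (r = 0) and .78 (r = .6) under like controls.

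The error is confined to that sentence and the reading it invites. The power claim for f² = .13 is sound, and the study remains well powered if effects are as large as those cited. It should be fixed because it is the plan's stated detectable effect, but it does not undermine the design.

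**What to change.** Keep N = 75, the analysis and the f² statement, and make one of two changes in section J:

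- Replace the d of .61 with a difference of about 0.76 residual SDs between the intervention group and each control group, assuming the two controls are alike; or
- Keep .61, say that it is in unadjusted within-group SD units, and state and justify the covariate–outcome correlation of about .60 that it needs.

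The description as medium can stay if it is attached to f² = .13. If the comparison with 1.11 and 1.12 is kept, state the SD basis on both sides.

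A supplementary sentence would also help: the .80 is for the 2-df test that the groups differ, whereas at d = .765 the chance that both single contrasts are significant is about .64 (simulated, t tests on 71 df). The correction does not depend on this addition.

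The cost is wording only. The stated detectable d becomes less favourable.
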